The IOM report *Dying in America* acknowledges the need to facilitate meaningful conversations with patients, families, and caregivers to promote awareness, raise expectations about care options, and have open exchanges about end of life (EOL).¹ Such conversations are infrequent in nursing homes² and even rarer for persons with mild to moderate dementia (Alzheimer's disease and other dementias, or ADRD) even though the majority (67%) of persons with dementia die in this setting.³ Consequences of not having these conversations include residents not receiving the care and treatment they want, as well as family distress, uncertainty, or conflicts due to residents' unknown wishes in the face of needed family decision making.⁴⁻⁵ Only once family and nursing home staff become aware of residents' preferences can care be truly person-centered and congruent with resident wishes. We have developed and demonstrated feasibility for an innovative systematic intervention—**Me & My Wishes**—that communicates residents' preferences via personalized video recorded conversations. *Me & My Wishes* are videos of nursing home residents talking about their preferences for care, and include four sections: About Me, Preferences for Today, Preferences for Medical Intervention and End of Life, and Afterthoughts.⁶ Videos are approved by the resident, and shared with nursing home staff and family.

The long-standing challenge for U.S. nursing homes is to provide high-quality care tailored to the unique needs and preferences of the 1.4 million older adults who live and die there.^{7,8} Studies indicate that nursing home quality of care can be suboptimal with deficits in staff training and support, symptom management, treating residents with dignity and respect, and communication.⁹⁻¹² Contrary to what many care providers believe, persons with mild to moderate dementia can accurately express their everyday and EOL preferences.¹³⁻¹⁶ Our feasibility study included these individuals and demonstrated that they were capable of communicating their

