preferences in the videos. Including individuals with mild to moderate cognitive limitations in advance care planning discussions and expressing their EOL preferences is warranted, viable and an ethical approach.^{13,14} Incorporating Me & My Wishes into the care planning process is expected to provide an efficient and effective way for residents to communicate their care preferences for today and at EOL, and to positively influence confidence in communicating preferences and in facilitating documentation of care planning documents.

Our long-term goal is to scale and fully incorporate Me & My Wishes into multiple settings providing long term services and supports. Ultimately, integrating Me & My Wishes videos into the electronic health record or another platform allows for video viewing by multiple individuals and disciplines in various settings. Our short-term goal, and the goal of this proposal, is to conduct Stage II efficacy testing of Me & My Wishes. We will employ a randomized wait-list control design of six nursing homes (48-54 residents). Three nursing homes will be assigned to an early intervention group (residents will share videos initially) and three assigned to the wait-list controls (residents will delay sharing videos). Videos can be viewed two ways: 1) in resident quarterly care conferences; and 2) via a secured web-based link for resident-identified family members. After video viewing, the resident, family and staff can discuss key messages and preferences of the video and add to the care plan.

Specific Aim 1: Examine the efficacy of the Me & My Wishes intervention among a sample of nursing home residents with dementia.

Hypothesis 1: Compared to the waitlist control group (Group 2), the intervention group (Group 1) will have an increase in the proportion of residents with documented goals of care discussions or self-reported conversations about preferences 90 days post video viewing.

Specific Aim 2: Examine self-efficacy of communicating preferences among residents with dementia, informal (family) and formal (staff) caregivers.

Hypothesis 2: Compared to the waitlist control group (Group 2), the intervention group (Group 1) will have greater self-efficacy scores for communicating preferences 90 days post video viewing.

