Me & My Wishes is a project that will study and develop a new approach to assist talking about the care preferences of long-term care residents, like yourself, by creating a video recorded conversation. Knowing what residents want and don't want is essential for facilities to provide quality care, and it also helps others to understand your wishes. We are doing this project because research studies have shown that asking about resident preferences and then communicating those preferences to staff and family members is challenging. Recording the conversation on video provides an efficient and effective way for residents to communicate their care preferences, and may align the care they receive with those wishes. The conversation will include preferences for today and for end-of-life care, and we are giving participants the option to share their videos with the facility staff and/or their families if they choose.

Barriers to Recruitment and Enrollment:

- mistrust
- medical concerns
- indifference
- sensory and cognitive limitations
- frail health
- restrictions to eligibility
- lack of confidentiality
- fear of safety
- scheduling conflicts
- lack of knowledge
- language/cultural differences

- inability or unwillingness of researchers to understand community dynamics and establish positive relationships with community members and leaders

Indifference, disinterest and wavering are the most common barriers in this process.
Preparing for such comments as:

"I don't think I care about this topic."
"I'm too tired/old for this."
"I'm too busy."
"This doesn't sound like something that would benefit me."
"I don't know. Is anyone else doing it?"
"Do you think I should?"
"I don't speak well."
"I don't like to be photographed."

... might help the RA to respond in a productive and positive manner. Potential responses may include:

"I want to make sure I explained clearly. Could you tell me what we are asking you to do?"

"I want to make sure I was clear about the pros and cons of participating in this study. Could you tell me what we are asking you to talk about on the videos?"

"Would you like me to come back another time?"

If resident declines

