- The hard copy will be kept in a locked cabinet and will be transferred to RedCap which is password protected and in an encrypted computer
- Only PI, co-investigators and research team will have access to the extracted data
- The de-identified extracted data will be stored in a locked cabinet at the College of Nursing.

List of data/information to be extracted from the resident chart:

- Age
- Gender
- Education
- Pay source
- Marital status
- Insurance
- Diagnoses
- Mood
- Level of care
- Length of stay
- Presence of documents such as Advance Directives, POLST, or Code Status
- Presence of goals of care conversations (may be found in nursing/social services notes). Document location of where found on form (facilities may differ on where this type of information is located).

Tips where to look for the data in the EHR:

- Demographic form
- Kardex
- Care plan
- Face-sheet
- MDS
- Documents
- *Refer to FAQ for more tips

Frequently Asked Questions (FAQ) during data extraction time:

1. I cannot find information about education anywhere in the chart?

This is common. You can ask the resident after video recording.

2. I found the racial background information but not the ethical background on the chart?

You can ask the resident about her or his ethnic background before video recording begins.

3. What is the difference between 'pay source' and 'Insurance'?

The demographic and clinical form gives you option about what to fill out. Most NH residents have Medicaid and/or Medicare. But you will need to find that information in the chart. And then you will need to see if the resident also have other private insurance (e.g. Elderplace or a type of Medicare Advantage).

4. The resident has a list of diagnoses (old and current) and I'm not sure if I need to write each one of them on the form?

Include at least 10 diagnoses on the form. If available, you can ask a clinician which are most relevant. You may have to make a judgment call about which DXs to include.

5. I found several admission dates on the chart; which ones do I write on the form?

We will collect the initial admission date and the *most recent* admission date, look at the chart carefully and make sure you have the correct dates. If the original date and most recent date is the same, enter the same date for both.

6. Do I count the length of stay from the most recent admission date?

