- ❖ Chain of Custody Documentation
Use the Chain of Custody forms to document exchange of the audio recorders, laptops and video equipment. The form must be filled out completely, including the name of the person in custody of the equipment and the dates in which the possession occurred.

Withdrawal of Participation / Attrition

Document any withdrawals of participation in REDCap along with reason.

Chapter Four

Administering Surveys

Surveys will be administered to residents, staff and family at three time points (baseline, sharing/within 72 hours of sharing, and 90 days post sharing).

Resident Surveys

The Resident Baseline Survey will need to be collected at the time of enrollment and read aloud to the resident. Follow same procedures for time of sharing and 90-day surveys.

Care Conference Staff Surveys (Time of sharing the video)

The Care Conference Staff Baseline Survey is provided at the time of enrollment (at a staff meeting or care conference prior to video sharing).

Family Surveys

The family baseline survey will need to be completed at the time of enrollment. Except for consent, follow same procedures for completing time of sharing and 90 day surveys.

Care Conference Staff and Family Compensation

Facility staff and family members are compensated with a \$5 gift card following the completion of each survey taken. If family are not present at care conference, their gift card can be mailed/mailed.

Care Conference Audio Recording and Data Collection Procedures

Care conference at the time of sharing will be audio-recorded using two audio recorders.

Most likely, staff and family caregivers will have completed the consent process at the time of the care conference meeting when the video is shared. In the event that an individual has not been consented (e.g. new staff to the care conference team), we will meet with the individual in a private space to review the recruitment letter and caregiver consent and upon agreement the informed consent process will be completed prior to starting the meeting.

Care Conference Video Sharing and Survey Collection Guidance

Briefing points for team member facilitating video sharing and discussion

- SC turn on/off 2 audio recorders.
- Let participants know video is approx. 20min, opportunity for discussion at end of video facilitated.

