**National Clinical Trial (NCT) Identified Number: NCT03861429**

**Principal Investigator: [name] NHA**

**Sponsor: University of Utah**

**Grant Number: R21AG058094**

**Funded by: NIA**

**Statistical Analysis Plan**

**August, 1, 2019**

## Randomization

We will employ a randomized wait-list control design with nursing homes and assisted living facilities. We block randomized five nursing homes and three assisted living communities in the Pacific Northwest into two groups based on size, proportion of residents with Medicaid, and proportion of residents with mild to moderate cognitive impairment. In Group 1 (early intervention group) NHs, videorecording, editing, and viewing will occur within three months of baseline. In Group 2 (delayed sharing) NHs, residents will be on a wait-list; after the delayed start, their video will be produced and viewed within three months.

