## Primary & Secondary Outcomes

We will calculate summary statistics for baseline demographics by intervention group, to assess comparability of groups and validate randomization scheme. We will use mixed modeling to compare the outcome measures goals of care discussions and self-efficacy of communicating preferences between Group 1 (early intervention) and Group 2 (wait-list) at 3 time points. Our specific model will be:  $Y = B_0 + B_1X + B_2T + B_3(X \cdot T) + e$  where, Y= goals of care discussions or self-efficacy of communicating preferences, X = Treatment condition (Group 1 vs. Group 2), T = Time point (baseline, 3 months, 6 months). Evaluation of the fixed effect of Treatment condition will tell us whether the two groups differ on average across all time points. The fixed effect of Time will tell us whether goals of care discussions change over time. Evaluation of the interaction of Treatment by Time will tell us if the groups change differentially, and will be the effect of primary interest.

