## Goals of Care

We analyzed results with an intent to treat approach using SPSS Version 24.0 (SPSS, Armonk, NY). Multilevel logistic regression (generalized estimating equations [GEE] with an autoregressive (1) working correlation matrix, logit link function) were fitted to assess the primary hypotheses. The models account for the repeated measures (3 or 4 time points), correlated, data structure per person. An additive model was conducted with contrast coding for each time point, treatment, and follow-up effects.

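### Does the SAP leave Hypothesis 1 untested by naming only goals of care discussions, when the protocol also counts self-reported conversations?

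*Protocol*

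**What the plan says.** **Protocol, Chapter Two, Specific Aim 1.** Hypothesis 1 concerns the proportion of residents with "documented goals of care discussions or self-reported conversations about preferences 90 days post video viewing". It is the only hypothesis under that aim.

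**SAP, Primary & Secondary Outcomes.** The model's outcome is defined as "Y= goals of care discussions or self-efficacy of communicating preferences". Self-reported conversations are not named.

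**SAP, Goals of Care.** The analysis is a GEE with an autoregressive working correlation and a "logit link function) were fitted to assess the primary hypotheses", over three or four time points. The section does not say which records score a resident as a yes.

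**Data sources.** In Protocol Chapter Three, Chart Review, the items to be taken from the chart include "Presence of goals of care conversations (may be found in nursing/social services notes". The chart is read after consent and before filming, and again at 90 days (question 10 of that section's FAQ). Chapter Four gives the surveys of residents, staff and family at baseline, then "sharing/within 72 hours of sharing, and 90 days post sharing".

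**The concern.** The hypothesis names two sources and the SAP names one. If the SAP meant the chart alone, its analysis would not test Hypothesis 1 as written. If it meant either source, a reader could not tell whether a result reflects charting, residents' own reports, or both. With about 48 residents, the choice could decide significance.

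A second worry follows if self-report does count. The intervention communicates residents' "preferences via personalized video recorded conversations", and the example recruitment statement describes "talking about the care preferences of long-term care residents, like yourself, by creating a video recorded conversation". For Group 2 the SAP's Randomization section says that "after the delayed start, their video will be produced and viewed within three months". If the survey item accepts the filming session as a conversation about preferences, only Group 1 could report it at a comparison made before Group 2 is filmed. A difference could then appear with no change in ordinary care.

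**Working it through.** **1. The plan's own figure.** The SAP's Power and Sample Size section gives a detectable effect of f = .213 with N = 48, 2 groups, 3 time points, correlation .5, power .90 and alpha .05. For the within-between interaction, λ = f²·N·m/(1−ρ) = .213² × 48 × 3/.5 = 13.07, with 2 and (48−2)×2 = 92 degrees of freedom. Power is 0.8998, so the figure reproduces. It does not depend on how the goals-of-care variable is scored, so it cannot settle the question.

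**2. The wording side by side.**

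| Feature | Hypothesis 1 | SAP |
|---|---|---|
| Unit | one proportion of residents | binary outcome per resident (logit link) |
| Label | documented discussions or self-reported conversations | goals of care discussions |
| Tie | the sole Aim 1 hypothesis | fitted to the primary hypotheses |

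A single proportion with an or inside it is met when either condition is met. Reading it as two separate endpoints is possible but strained. The SAP models a yes/no outcome and points it at the primary hypotheses, which fits shorthand for the same variable.

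**3. Does the chart list point to the chart alone?** No. That list is headed as data to be taken from the chart, so it could hold only chart items. The timing leans the other way. Chart extraction is described at two points (initial and 90 days), resident surveys at three, and the Goals of Care model uses three or four.

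**4. Effect of the definition on power.** All rates are assumed, because the documents give none. The settings are 24 per arm (48/2), two-sided .05, Fisher's exact test, one time point and no clustering. With charted rate c and self-report rate s, the either-counts rate is 1−(1−c)(1−s) if the sources are independent, max(c, s) if nested, and c+s if disjoint.

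| Assumed change | Charting alone | Either counts |
|---|---|---|
| c 20%→60%, s 30% unchanged, independent | 76% | 41% (44% vs 72%) |
| same, nested | 76% | 47% (30% vs 60%) |
| same, disjoint | 76% | 83% (50% vs 90%) |
| c 20%→60%, s 30%→60%, independent | 76% | 78% (44% vs 84%) |
| c and s both 20%→50%, independent | 49% | 73% (36% vs 75%) |

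The composite can lose or gain power. The direction depends on overlap and on whether self-reported conversations also rise, as the intervention intends.

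**5. Filming recalled as a conversation.** If a share r of residents count the session, p₁ = p₀ + (1−p₀)r. With p₀ = 30% and no true change:

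| r | p₁ | Chance of significance |
|---|---|---|
| 10% | 37% | 5% |
| 20% | 44% | 11% |
| 40% | 58% | 41% |
| 60% | 72% | 80% |

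At r = 40% the chance is 55% if p₀ = 20% and 15% if p₀ = 60%. These figures need four conditions together: self-report enters, the item accepts the session, residents recall it, and Group 2 is unfilmed at the comparison. On the last, the protocol's Chapter Two says only that wait-list residents delay sharing. On recall, the nominal timetable is two weeks to consensus, two weeks of editing and 90 days after sharing: 14 + 14 + 90 = 118 days, in residents with dementia. Those are schedule targets, not minimum intervals. The planned GEE is also a different comparison. It uses contrast coding for time, treatment and follow-up, and the worked example of that coding in the SAP's Concordance Analysis section scores wait-list residents as treated once they share.

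**The case for a change.** The strongest case for a change is that an outcome definition belongs in the SAP. Self-report appears nowhere in it, Hypothesis 1 is not cited by number, and no rule covers a resident with one source missing. The same assumed charting gain gives 41%, 47% or 83% power on the composite depending on overlap alone, which is a wide range for a trial of this size. A definition and a split of data already planned would cost little.

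The textual part of this stands: the SAP does not restate the two sources or how they combine. The inference from it is weaker. The hypothesis supplies the rule, and the SAP's model form and stated purpose agree with it. The power range shows that the definition matters, not that the plan has chosen wrongly. Separate reporting of the two sources would be informative, but it is an added analysis and corrects nothing. The filming concern is fair to raise. It is unproven, however, because neither the survey items nor the Data Code Book is among the documents.

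**Conclusion.** No change to the plan is needed. The SAP uses a short label for an outcome that the protocol spells out, and an analyst working from Hypothesis 1 would score a resident as a yes when either source is present. This rests on reading the or in its ordinary sense and on the Goals of Care model being the test of Hypothesis 1.

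The numerical consequence cannot be fixed from the documents. Under assumed rates, either-counts scoring moves power from 76% to 41% in one case and from 49% to 73% in another. The filming effect runs from negligible at 10% recall to large at 60%, but only if all four conditions hold and only for a single-time comparison that the SAP does not plan. Survey wording that expressly counted the filming session would reopen that part; nothing in the documents shows that it does.

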 - Conversations are not often passed on to others or recorded.
 - Preferences for care today and at the end-of-life can be a difficult topic to discuss.
 - When they do occur, conversations often happen too late or at times of crisis or transition such as hospitalization.
 - Advance Care Planning (ACP) is associated with higher quality of life and satisfaction with care.
 - ACP is also associated with decreased rates of depression and anxiety among bereaved loved ones.
 - Lack of ACP often results in more invasive care than is desired.
- Reviewing the consent forms and obtaining consent from those who wish to participate.
- Scheduling the date video recording will take place and informing NH staff, as well as other scheduling.
- Performance of the Chart Review and completion of the Demographic and Medical Record Review Forms as described later in this chapter.

Staff, Family and Resident Recruitment

Staff Consent

- ❖ Care Conference Staff
Care Conference Team Consent Letter (Appendix F)

Care Conference Staff Consent

Recruitment of staff members will occur in person. The care conference team members of the resident will receive a recruitment letter and staff caregiver consent either in person or via email stating the purpose of the study or at a staff meeting or care conference prior to video sharing. The SC will explain the study, review the IRB-approved informed consent document, and answer any questions the care conference team member might have. Ample time will be provided for the staff member to consider participation. A follow-up visit can be readily scheduled by the SC. For staff members who agree to participate, we will document affirmation of consent. Potential interdisciplinary care team participating in care conference will be nurse manager, social services director, dietary manager, nurse's aide

Strategies for Communicating Research to Staff Members.

Information session in standup meeting

Attend Resident Council Meeting

Attend All-Staff meeting

Approach staff members 1:1 on scheduled time

- May include positive testimonials if applicable

Me and My Wishes: Study Stand-Up Checklist

- NH Champion preferred day/time to meet weekly/bi-weekly (obtain more than one date since we will be juggling a few facilities).
- NH champion's preferred introduction schedule. Do they prefer to introduce SC's to residents all at same time or separately after each consent?

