- NH champion speaks to resident with no bias introduced (such as "this resident would be a good person for this study").
- Only SC's explain MMW study to resident.
- Does NH champion know of any additional people coming to care conference that are not aware of study?
- When calling NH champion confirm residents are available for consenting/video recording.
- Ask if there are any recent admissions that would meet criteria.

Family Consent and Survey Scripting

A recruitment letter and a copy of family caregiver consent will be sent either by mail or email to the family members identified by the resident stating the purpose of the study and that a follow-up phone call will be made. The letter will include information of who to contact if they wish to opt out. If the family member declines we can ask the resident if they want to share the video with anyone else

- ❖ Family (process for contacting/recruitment)
Family Recruitment and Consent Letters (Appendix G)
Family Sub Study Consent Letter (Appendix G1)

This process should be practiced with a member of the MMW team prior to live implementation.

Hello is this (family member's name)?—response.

This is (your name) from the University of Utah College of Nursing and the Me & My Wishes project. I am calling to verify that you received the letter about the project and to see if you have some time today to learn more about the project. Is this a good time?—response.

At this point in the conversation please refer to the *Family Consent Cover Letter*. Proceed by reading the first two paragraphs of the consent.

Does this sound like something that you would be interested in?—response.

If yes: Great, thank you. Let's take the next few minutes to review more details about the study, your participation, and obtain your consent to participate. If you would like, I can send you a copy of the consent via mail/email?—response.

Do you have 15-20 minutes now to go over the initial survey?—response.

Proceed to the family baseline survey.

Do you have any questions?—response. (answer questions). If mail/email address is not known, obtain for the purposes of sending \$5 gift certificate.

Outline the next steps for the participant.

As mentioned in the consent you may watch your family member's/friends personal video by attending care conference at the facility or at the time that we share the video I can send you a link to view the video from your home computer and complete a brief survey.—response.

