## Power and Sample Size

Sensitivity analysis was conducted with G-Power 3.1. With a proposed sample size = 48, 2 Groups, 3 timepoints, correlation between time points = .5, power = .90, and alpha = .05, we will be able to detect a medium effect size  $f = .213$  using a general linear modeling of repeated measures looking for within-between subjects' interaction. T= Time point (baseline, 3 months, 6 months).

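### The example recruitment statement tells residents the video works, and staff may hear testimonials, which may add expectancy to self-rated outcomes in an open wait-list trial

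*Protocol*

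**What the plan says.** **To residents.** Protocol Chapter Three, Resident Recruitment, suggests writing down a general statement for research staff to use and gives an example. One sentence in it reads "Recording the conversation on video provides an efficient and effective way for residents to communicate their care preferences". The rest of that sentence is hedged: the video may bring care into line with the resident's wishes. The example also opens by calling the project one that will study a new approach.

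**To staff.** In the same chapter, the list of strategies for communicating the research to staff members includes "May include positive testimonials if applicable".

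**What is under test.** Specific Aim 1 is to "Examine the efficacy of the Me & My Wishes intervention among a sample of nursing home residents with dementia". Chapter Two (Communication Tool for Care Preferences) gives testing efficacy as the goal. Its Stage II Efficacy section uses almost the same phrase as the resident statement, but only as an expectation.

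**Who rates what.** Hypothesis 2 compares self-efficacy scores under an aim that covers residents, family and staff. Hypothesis 1 counts either documented goals-of-care discussions or self-reported conversations. Hypothesis 3 rests on documents.

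**Design and data collection.** The SAP (Randomization) allocates facilities to early or delayed sharing with a wait-list. Neither document describes blinding. The coordinators recruit, collect data and film the videos. Resident surveys are read aloud, starting at enrolment (Chapter Four). In the SAP (Primary & Secondary Outcomes) the effect of primary interest is Treatment by Time: "Evaluation of the interaction of Treatment by Time will tell us if the groups change differentially".

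**The concern.** The asserted benefit, that video is an effective way to communicate preferences, lies very close to what Hypothesis 2 measures: self-efficacy for communicating preferences. Participants who have been told the product works, who then either receive it or wait for it, and who rate themselves, can report improvement because they expect it. Resident answers are spoken aloud, possibly to the team that made the claim. The protocol itself notes (Chapter Three, If resident declines) that participants may worry about what the researcher wants.

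At stake is how a positive Hypothesis 2 result, or a positive Hypothesis 1 result driven by self-reported conversations, would be read. Some of the difference might be expectancy rather than better communication, and the planned analysis cannot separate the two.

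**Working it through.** **1. Does the wording conflict with the trial's purpose?** Three statements of the same benefit stand side by side. The goal in Chapter Two treats efficacy as unknown. The rationale in Stage II Efficacy treats it as expected. The example resident statement treats it as established. Only the third departs from the trial's premise.

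**2. When could it reach the effect of primary interest?** Nothing says the message differs by arm, and the resident baseline follows it. A shift shared equally by both arms, or present from baseline onward, gives a Treatment by Time effect of zero. Bias needs a shift that appears after baseline and is larger in one arm. That is possible because Group 1 receives the product while Group 2 waits.

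**3. Reproduce the plan's own figure.** Inputs from the SAP, Power and Sample Size: "With a proposed sample size = 48, 2 Groups, 3 timepoints" and "correlation between time points = .5, power = .90, and alpha = .05", with detectable f = .213 for the within-between interaction.
- Noncentrality: λ = f² × N × m / (1 − ρ) = .213² × 48 × 3 / .5 = 13.07.
- Degrees of freedom: (2 − 1)(3 − 1) = 2 and (48 − 2)(3 − 1) = 92, sphericity assumed.
- Power = 0.8998, so the stated .90 is reproduced. Solving for power .90 gives f = 0.2131.

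**4. Illustrate a differential expectancy shift with no true effect.** Let expectation raise Group 1 above Group 2 by d SD at both follow-ups.
- The between-arm difference over time is (0, d, d). Centred on its mean 2d/3, it is (−2d/3, d/3, d/3). Halved between two arms, the interaction effects have size d/3, d/6 and d/6.
- f² = (d²/9 + d²/36 + d²/36) / 3 = d²/18, so f = 0.2357d.
- λ = (d²/18) × 288 = 16d², where 288 = 48 × 3 / .5.
- A shift at 3 months only, (0, d, 0), gives the same f.
- A shift that builds linearly, (0, d/2, d), gives f² = d²/24 and λ = 12d².

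| Assumed d (SD) | f, sustained | λ, sustained | P(significant), sustained | P(significant), linear |
|---|---|---|---|---|
| 0 | 0 | 0 | 0.050 | 0.050 |
| 0.1 | 0.024 | 0.16 | 0.062 | 0.059 |
| 0.2 | 0.047 | 0.64 | 0.100 | 0.087 |
| 0.3 | 0.071 | 1.44 | 0.169 | 0.137 |
| 0.5 | 0.118 | 4.00 | 0.404 | 0.312 |

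A sustained shift of .213 / 0.2357 = 0.90 SD would be needed to equal the plan's detectable f.

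**5. Cross-check on a single change contrast.** With 48 / 2 = 24 per arm, SE = √(2 × 2 × (1 − .5) / 24) = 0.289. Shifts of 0.1, 0.2 and 0.3 SD give rejection probabilities of 0.064, 0.107 and 0.180, in line with the table.

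**6. Limits of the illustration.** The values of d are assumptions: the documents give no SD and no expectancy effect. Each d is the total differential expectancy, not the share due to this wording. The calculation applies to residents and to a continuous score. It ignores clustering by facility and follows the SAP's sample-size method rather than the GEE models described later in the SAP.

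**The case against.** The strongest reply is that both arms hear the same words before the resident baseline, so the wording cannot by itself separate the arms. Differential expectancy comes from known allocation combined with self-rating, which any open wait-list trial has and which rewording leaves in place. This stands, and it limits the point to an avoidable addition to a risk that already exists.

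Several stronger readings are tempting but not supported:
- *A reader might infer that all coordinators must use this script.* The text is offered as an example, and the testimonials are a separate, optional staff item with no stated content.
- *A reader might infer that the coordinators break the plan's own no-bias rule.* The Study Stand-Up Checklist does say "NH champion speaks to resident with no bias introduced", but the example attached to it is recommending a particular resident as a good candidate. It does not address claims of benefit, so there is no clear contradiction.
- *A reader might infer that consent is compromised.* The example also contains hedged language, residents must pass a teach-back, and the consent document covers risks and benefits. That document was not available, so how it describes benefit cannot be judged.
- *A reader might apply the percentages to every Hypothesis 2 respondent group.* No family or staff sample size is given. The family telephone script makes no effectiveness claim.

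That the trial is open is itself inferred from the wait-list design and the absence of any blinding text.

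**Conclusion.** The point holds as a modest, inexpensive improvement. The example statement presents as settled what the trial is testing, and the optional testimonials carry a similar message to staff who will rate themselves. With a wait-list control and no described blinding, this may add to differential expectancy after baseline in resident and staff self-efficacy and in self-reported conversations under Hypothesis 1.

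Hypothesis 3 and the documented part of Hypothesis 1 are unaffected, because they are not self-ratings.

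The size is unknown. For residents, under the SAP's inputs and an assumed sustained differential shift of 0.2 to 0.3 SD with no true effect, the false-positive rate would be about 10% to 17% instead of 5%. This rests on independent residents, sphericity and a correlation of .5. It is a range for scale, not an estimate of what this wording does. The documents do not support saying that any observed difference *is* expectancy created by the wording, only that some of it *may* be.

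**What to change.** - **Resident Recruitment, example statement:** replace the sentence asserting effectiveness with neutral wording, for example: *We do not yet know whether recording the conversation helps; this study is testing that.*
- **Strategies for Communicating Research to Staff Members:** delete the testimonials line for staff who will complete surveys.

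The cost is a minor IRB amendment and possibly slightly less recruitment appeal. Sample size and analysis do not change. The change reduces the expectancy risk of an open design but does not remove it.

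Parts of the SAP are written in the past tense. If enrolment has already closed, state in the trial report what residents and staff were told, and name it as a limitation on Hypothesis 2 and on the self-reported part of Hypothesis 1.
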